5.5.8.5. Components of Voice Analysis

To evaluate speech change associated with neuro-degeneration in patients with ALS, speech samples for voice analysis will be collected periodically using mobile app and analyzed using a computational model for speech production. The parameters of speech-based outcome can be classified in 3 domains (precision in speaking, vocal control, and speaking rate). Each parameter within the domains were summarized by Aural Analytics as follows:

Precision in Speaking

- **Articulation Entropy:** An aggregated measure of how ‘typical’ speech sounds are. For example, the score for the word more is a combination of the typicality of pronunciation for ‘m’, ‘o’ and ‘r’. All articulation entropy raw values are negative. Normal speech has articulation entropy close to 0. Articulation Entropy is more negative in imprecise speech, as is typical in advanced ALS patients.
- **Vowel Space Area:** A measure of how distinct vowel sounds are from each other. Typical speech has a large, positive vowel space area. Vowel Space Area decreases toward 0 as vowel sounds become less differentiated, as is typical in advanced ALS patients.
- **Low-Frequency Energy Distribution:** A measure of how much speech sounds are ‘nasalized’, sounding like ‘m’ or ‘n’. All values are negative; values closer to 0 are more nasalized, as often occurs in advanced ALS patients.
- **Low-Frequency/High Frequency Ratio:** Another measure of how much speech sounds are ‘nasalized’, sounding like ‘m’ or ‘n’. All values are negative; values closer to 0 are more nasalized, as often occurs in advanced ALS patients.

Vocal Control

- **Perceptual Loudness Decay:** Measures how quickly the voice loses energy when holding out the sound ‘aaaaahhh.’ Normal voices lose energy slowly and have decay values that are near 0. Values can be positive or negative. Larger negative values are associated with an inability to sustain speech, as occurs in advanced ALS patients.
- **Flutter:** A measure of involuntary movement (rapid tremor) in the vocal folds. Normal speech has 0 flutter. Greater than 0 flutter is associated with the type of vocal fold vibration that occurs in advanced ALS patients.
- **Phonatory Duration:** Measures how long a patient can hold out the sound ‘aaaaahhh.’ Longer, positive hold times are associated with normal voices; as the ability to hold out the vowel sound is lost, phonatory duration decreases toward 0.
- **Fundamental Frequency:** A measure of voice pitch. Low fundamental frequency indicates low pitch. Fundamental frequency is always greater than 0.
- **Fundamental Frequency Variability:** A measure of variability in voice pitch. Steadier voices have variability near 0; larger positive variability values indicate a more widely varying voice pitch.

Speaking Rate

- **Articulation Rate:** A measure of how quickly individual sounds in a word are spoken. Articulation rate is always greater than 0. Articulation rate closer to 0 indicates slower speech and is associated with more advanced ALS patients.
- **Articulation Rate Variability:** A measure of change in articulation rate over the course of a clinical session. Articulation rate variability can be positive or negative; more negative values indicate fatigue of muscles involved in speech.

- **Speaking Rate:** A measure of how quickly syllables in a word are spoken. Speaking rate is always greater than 0. Speaking rate closer to 0 indicates slower speech and is associated with more advanced ALS patients.
- **Speaking Rate Variability:** A measure of change in speaking rate over the course of a clinical session. Speaking rate variability can be positive or negative; more negative values indicate fatigue of muscles involved in speech.
- **Pause Rate:** A measure of how often patients need to pause for breath while speaking. Pause Rate is always greater than 0. A higher pause rate indicates that a speaker needs to pause for breath often, as is the case in advanced ALS patients.
- **Pause Rate Variability:** A measure of control over respiration, derived from the change in pause rate over the course of a clinical session. Pause rate can be positive or negative; more positive values indicate loss of respiratory control.

The speech-based outcome will be tracked within session and at each study visit over time. For each parameter, the longitudinal outcome collected at each study visit will first be normalized to adjust for background differences for individual patient, and be transformed as a percent change from baseline using the equation: $[(\text{post baseline value} - \text{baseline value}) / \text{baseline value}] \times 100$. For a domain, the outcome for analysis will be the average of the percent changes from baseline from all parameters within the domain.

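### SAP 5.5.8.5 averages signed percent changes within each voice domain without aligning direction, so worsening partly or fully cancels; percent change also fails at zero, near-zero or sign-changing baselines

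*SAP*

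**What the plan says.** SAP 5.5.8.5 groups the voice parameters into Precision in Speaking (four), Vocal Control (five) and Speaking Rate (six). Each parameter's values "will first be normalized to adjust for background differences for individual patient"; the method is not given. They are then turned into 100 × (post − baseline)/baseline. The last step is: "For a domain, the outcome for analysis will be the average of the percent changes from baseline from all parameters within the domain".

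The same section describes sign and direction parameter by parameter:

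- Articulation entropy: "All articulation entropy raw values are negative", and "Articulation Entropy is more negative in imprecise speech, as is typical in advanced ALS patients".
- Vowel space area: "Vowel Space Area decreases toward 0 as vowel sounds become less differentiated, as is typical in advanced ALS patients".
- Both low-frequency measures: "All values are negative; values closer to 0 are more nasalized, as often occurs in advanced ALS patients".
- Perceptual loudness decay: "Values can be positive or negative. Larger negative values are associated with an inability to sustain speech, as occurs in advanced ALS patients".
- Flutter: "Normal speech has 0 flutter".

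SAP 5.5.2 uses the same signed denominator and deals only with missing values. SAP 5.5.8.3 treats the muscle strength mega score, also a mean of percent changes, differently: a zero baseline is set to missing and the favourable direction is stated. The voice domain scores have neither provision.

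**The concern.** A composite can be interpreted only if its parts point the same way. Here they do not, and the plan contains no reversal, absolute-value denominator or weighting before the average. Followed exactly, it can give a domain score of zero, or of the wrong sign, for a patient who is worse on every parameter with a stated direction. The denominator is a second problem: several parameters are described as zero, near zero or of either sign in some patients, where percent change is undefined, unstable or reversed.

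At stake is the exploratory objective on speech production (SAP 2.1.3) and its change and slope endpoints (SAP 2.2.4). A treatment difference in a domain score may be diluted, absent or reversed relative to what the parameters show. Sign and scale choices made after unblinding would be open to the charge of being data-driven.

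**Working it through.** The documents give no voice data and no planned figure to reproduce. The check applies the SAP formula to the SAP's own descriptions. The worsening percentages are illustrative, expressed as a share of |baseline|, and assume that normalisation preserves sign and zero.

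**Sign of the percent change when a parameter worsens**

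| Domain | Parameter | Baseline | Worse means | Percent change |
|---|---|---|---|---|
| Precision | Articulation entropy | negative | more negative | + |
| Precision | Vowel space area | positive | towards 0 | − |
| Precision | Two low-frequency measures | negative | towards 0 | − |
| Vocal Control | Loudness decay | either sign | larger negative | + if baseline negative |
| Vocal Control | Flutter | 0 in normal speech | above 0 | +, undefined at 0 |
| Vocal Control | Phonatory duration | positive | towards 0 | − |
| Vocal Control | Pitch, pitch variability | positive; steady voices near 0 on variability | not stated | – |
| Speaking Rate | Articulation rate, speaking rate | positive | towards 0 | − |
| Speaking Rate | Variability of those two | either sign | more negative | − if baseline positive, + if negative |
| Speaking Rate | Pause rate | positive | higher | + |
| Speaking Rate | Pause rate variability | either sign (see below) | more positive | + if baseline positive, − if negative |

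**Precision.** With entropy worse by e and the others by d1, d2, d3, the score is (e − d1 − d2 − d3)/4.
- All 30% worse: (30 − 90)/4 = -15%. The sign is right and the size is halved.
- Entropy 60%, others 20%: (60 − 60)/4 = 0.
- Entropy 70%, others 20%: (70 − 60)/4 = +2.5%.
- The score is 0 or positive only if e ≥ d1 + d2 + d3, that is, if entropy worsens at least three times as much as the average of the other three.

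**Speaking Rate, all six 20% worse.** Articulation rate, speaking rate and pause rate contribute −20 − 20 + 20 = −20. Each of the three variability measures adds +20 or −20 according to its baseline sign.
- All three add: (−20 + 60)/6 = +6.7% (1 combination).
- Two add: (−20 + 20)/6 = 0 (3 combinations).
- One adds: (−20 − 20)/6 = -6.7% (3 combinations).
- None adds: (−20 − 60)/6 = -13.3% (1 combination).

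No combination gives -20%, and four of eight score 0 or better. The count rests on one reading. The Pause Rate Variability entry says that pause rate can take either sign, but pause rate itself is stated to be always above 0, so I take the remark to mean the variability measure. If that measure were always positive, the fixed part would be −20 − 20 + 20 + 20 = 0, and the scores would be +6.7% (1), 0 (2) and -6.7% (1).

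**Vocal Control.** Loudness decay with a negative baseline, flutter and phonatory duration each 20% worse, pitch measures unchanged: (20 + 20 − 20 + 0 + 0)/5 = +4%.

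**Denominators.** Take a parameter that can have either sign and for which lower is worse. A fall of 0.1 gives -10% from a baseline of +1, -1000% from +0.01, +1000% from −0.01 and +10% from −1; at 0 it is undefined. The SAP describes values near zero for normal loudness decay, steady pitch and normal articulation entropy. A fixed sign therefore does not exempt Precision from instability.

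**The case against.** **The normalisation, or the external supplier's specification, may already handle this.** Values are normalised first, and voice data arrive from outside in a pre-specified format (SAP 5.2). But the stated purpose of normalising is individual background differences, not direction. If it also aligns signs, the SAP needs to say so. What stands is that every figure here is conditional on unseen processing.

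**Parameter-level results are foreseen.** SAP 7.7 refers to slopes of percent change in voice parameters. These avoid cancellation but keep the zero, near-zero and sign-changing denominators. The graphical assumption check in SAP 7.1 might expose extreme ratios; it would not align signs.

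**The stakes are limited.** This stands. The endpoints are exploratory and outside the closed testing procedure (SAP 7.4). Because the arms are randomised, the composite does not by itself favour either arm when there is no effect; the loss is in power and interpretation.

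A reader might also infer more than the documents support:

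- That every domain score is uninterpretable. In Precision three of four parameters agree, and ordinary worsening is attenuated rather than reversed.
- That half of patients would score 0 or better in Speaking Rate. Four of eight counts sign combinations; no frequencies are given.
- That loudness decay falling from a positive value is worsening. The SAP places normal voices near 0 and calls only larger negative values abnormal.
- That the instability can be sized. No baseline distribution is given.

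**Conclusion.** The point holds. SAP 5.5.8.5 states no alignment of direction, and its own descriptions put opposing signs of worsening in all three voice domains. Cancellation is partial in the ordinary Precision case, and can be complete or reversed in Speaking Rate and Vocal Control under the conditions shown. Percent change is also undefined for flutter at zero, flips with the baseline for loudness decay and the three rate-variability measures, and is unstable near zero for loudness decay, pitch variability and articulation entropy.

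Confidence is high on the missing alignment. The figures rest on illustrative worsening and on normalisation that preserves sign and zero. No primary, secondary or safety result is affected. Fine Motor Fatigue (SAP 5.5.8.6) uses the same average and may share the problem, but the SAP states no worse direction for its parameters, so cancellation there cannot be shown. Tracing Error is a single, always positive parameter, and no defect is shown for it.

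**What to change.** Before database lock:

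1. Add a sign table, applied to the change itself, so that lower means worse. Sign +1: articulation entropy, vowel space area, phonatory duration, articulation rate, speaking rate, the variability of those two rates, and loudness decay in the negative range. Sign −1: both low-frequency measures, flutter, pause rate and pause rate variability. The sponsor sets a direction for pitch, pitch variability and positive loudness-decay values, or analyses these parameters singly.
2. For the domain averages, replace division by the patient's own baseline with a scale that is safe at zero. One option is change divided by the pooled baseline SD across all arms, with a matching composite baseline and SAP 7.7 model text to suit. Setting zero baselines to missing, as for the mega score, is not enough: it drops flutter for patients with normal speech and leaves near-zero and sign-changing baselines.
3. Define the normalisation, confirm that it changes neither sign nor direction, and say whether slopes are analysed by domain or by parameter.
4. Apply the same direction check to Fine Motor Fatigue. Leave Tracing Error on its present scale.

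The cost is one paragraph, a table and matching model text. Scores are no longer in percent, and a domain may shrink: Vocal Control falls from five parameters to three if both pitch measures are analysed singly, and to two if loudness decay is as well.

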5.5.8.6. Components of Handwriting Analysis

Fine motor assessments, including handwriting and figure tracing, will be performed using a stylus and mobile app. The parameters used in the handwriting analysis can be classified into 2 domains (fine motor precision and fine motor fatigue) and were summarized by Aural Analytics as follows:

Fine Motor Precision

- **Tracing Error:** Measure of deviation from traced line. All values are positive. Lines that closely match the trace will have low tracing error; lines that do not closely match the trace will have high tracing error.

Fine Motor Fatigue

- **Average Pressure:** Measure of pen pressure on writing surface. Pressure is always positive. The larger the value, the more pressure the user is applying to the surface of the iPad.
- **Average Pressure Decay:** A measure of the decay in pressure over time. A negative value indicates reduced pressure over time; this means that the user is applying less and less pressure over the duration of the task.
- **Average Speed:** Measure of pen speed over writing surface. Larger values indicate faster pen motion.
- **Average Speed Decay:** A measure of the decay in speed over time. A negative value indicates greater reduction in speed over time; this means that the user is becoming slower and slower over the duration of the task.

- **Average Acceleration:** Measure of pen acceleration on the writing surface. Larger values indicate higher pen acceleration.
- **Average Acceleration Decay:** A measure of the decay in acceleration over time. A negative value indicates greater reduction in acceleration over time. This means that the user’s acceleration is changing less and less over the duration of the task.
- **Average Tracking Jerk:** A measure of change in the pen’s acceleration over the duration of the tasks. This captures ‘jerking’ behavior where the pen doesn’t glide smoothly across the tablet surface but rather exhibits ‘stop-go’ behavior.

The fine motor assessments will be performed at all study visits. For analysis, the longitudinal data collected from each patient will be transformed as a percent change from baseline using the equation: $[(\text{post baseline value} - \text{baseline value}) / \text{baseline value}] \times 100$. For a domain, the outcome for analysis will be the average of the percent changes from baseline from all parameters within the domain.

5.5.8.7. ALS Assessment Questionnaire Short Form

The ALSAQ-5 is a subjective health measure designed to assess the health-related quality of life in patients with ALS (Jenkinson 2001). It is a short form of ALSAQ derived from ALSAQ-40 that includes 40 items evaluating 5 dimensions of health status that are affected by the disease: physical mobility (10 items), activities of daily living and independence (10 items), eating and drinking (3 items), communication (7 items), and emotional reactions (10 items).

The ALSAQ-5 includes five selected items with one item representing each dimension. It produces results closely resembled those of the five dimension scores of the ALSAQ-40. The dimensions and the corresponding items for ALSAQ-5 are shown in Table 3.

Patients are asked to select one of the five options according to the frequency of each event experienced during the last two weeks, and a score is assigned for each option: 0=never, 1=rarely, 2=sometimes, 3=often, 4=always or cannot do at all.

Table 3: Dimensions and Items of ALSAQ-5

Dimension	Item (Question) for ALSAQ-5
physical mobility	Q1: I have found it difficult to stand up.
activities of daily living and independence	Q2: I have had difficulty using my arms and hands.
eating and drinking	Q3: I have had difficulty eating solid food.
communication	Q4: I have felt that my speech has not been easy to understand.
emotional functioning	Q5: I have felt hopeless about the future.

The score of item for each dimension is then transformed on a scale of 0 to 100 using the equation: $(\text{score of each dimension}/4) \times 100$, with 0 indicating perfect health and 100 indicating worst possible health status. The interpretation of the score is shown in Table 4.

Table 4: Interpretation of Score Ranges for Dimensions on ALSAQ-5

Score range	Interpretation
0 –19	No problems
20-39	Problems rarely
40-59	Problems Sometimes
60-79	Problems Often
80-100	Problems always/ nearly always or unable to do at all

Source: [Jenkinson 2001](#)

The ALSAQ-5 total score is calculated as sum of the score from the 5 individual items, and the total score will be set to missing if any of the score among the 5 items is missing.

5.5.9. Health Economic Outcome Measures

If a patient is prescribed and agrees to receive any of the following during the course of the study, the date of prescription will be recorded:

- Non-invasive ventilation
- Gastrostomy tube
- Manual wheelchair
- Power wheelchair
- Augmentative and alternative communication

5.5.10. Safety and Related Data

5.5.10.1. Exposure and Compliance

Information of whether a patient received a scheduled dose will be recorded.

5.5.10.2. Adverse Event

AE Duration

The duration (in days) of an adverse event (AE) is calculated as AE stop date - AE start date + 1. If the event is ongoing, the final database lock date will be used as the stop date in duration calculations.

AE Severity

The severity of an AE is based on the Common Terminology Criteria for Adverse Events (CTCAE) grades collected on the CRF:

Grade 1 = Mild

Grade 2 = Moderate

Grade 3 = Severe

Grade 4 = Life threatening

Grade 5 = Fatal

For summary purposes, missing severity will be counted as severe.

AE Relatedness

All AEs classified as treatment related by the investigator on the CRF are considered treatment related. For summary purposes, missing relatedness will be counted as related.

TEAE and Serious TEAE

An AE or serious AE (SAE) will be regarded as treatment emergent if it starts or worsens (eg, increases in severity or frequency) during or after the first dose of study drug.

Death

Date and reason of death will be recorded and presented.

5.5.10.3. Clinically Relevant Abnormalities in Vital Signs, Weight, and ECG

The criteria used to identify clinically significant abnormalities in vital signs are given in [Table 6](#). The criteria used to identify clinically significant abnormalities in ECG are given in [Table 7](#).

5.5.10.4. Prior and Concomitant Medications

The prior and concomitant flags for medications other than study treatment will be derived. Medications with a stop date prior to the first dose of study drug will be considered prior medications. Medications with a stop date on or after the first dose of study drug will be considered concomitant medications.

5.5.10.5. Beck Depression Inventory

The Beck Depression Inventory (BDI[®]) – Fast Screen (BDI-FS) is a shortened version of the BDI-II that evaluates key symptoms of depression. It was developed to factor out co-occurring depression symptomatology that may be related to a medical condition ([Steer 1999](#)), and concentrate on factors of depression that relate solely to depression. The BDI-FS contains 7 self-reported items that evaluate major depressive symptoms over the past 2 weeks, including sadness, pessimism, past failure, loss of pleasure, self-dislike, self-criticalness, and suicidal ideations ([Beck 2000](#), [Steer 1999](#)). Individual scale items are scored on a 4-point continuum (0=least, 3=most), with a total summed score range of 0–21. Higher scores indicate greater depressive severity. Patient's depression level will be classified using the BDI total score as shown in [Table 5](#). The BDI total score will be set to missing if an answer to any of the 7 items is missing.

Table 5: Depression Level Classification by BDI Total Score

Depression Level	BDI Total Score
Minimal Depression	0 - 3
Mild Depression	4 - 6
Moderate Depression	7 - 9
Severe Depression	10 - 21

5.5.11. Pharmacokinetics Parameters

The PK parameters are defined as follows:

Parameter	Definition
AUC_{0-t}	Area under the concentration-time curve from time zero to the last measurable concentration, also called AUC_{last} .
$AUC_{0-\tau}$	Area under the concentration-time curve from time zero to time τ (eg, hours). It is calculated by using the trapezoid rule if all concentrations are above quantitation limit before time τ , and by using extrapolation if concentration drops below quantitation limit before time τ .
C_{max}	The maximum (or peak) concentration that a drug achieves in tested area after the drug has been administrated and prior to the administration of next dose.
C_{trough}	The minimum concentration between dose time and dose time + τ (at T_{trough}).
t_{max}	The time that C_{max} was observed.

The parameters C_{max} , AUC and t_{max} will be derived using the following rules:

- For calculation of C_{max} , pre-dose value will not be included in the determinations.
- Analyses will be based on actual sampling time converted to elapse time defined as time from dosing.
- Any concentration below the lower limit of quantitation (LLOQ) will be reported as 0.00 for summaries by each time point.
- For AUC calculations, samples with values below the LLOQ prior to the first measurable concentration will be set to zero. Samples with below the LLOQ result after the first measurable concentration will be treated as missing and the calculation of AUC will proceed by fitting a trapezoid between the surrounding, non-missing values.
- t_{max} will be calculated only for patients who have at least two samples collected after dosing.

At Weeks 2 and 12 PK samples will be collected at pre-dose, and 1, 3 and 6 hours post-dose. For AUC₁₂ calculation, the pre-dose concentration will be used to approximate the concentration value at 12 hours.

